	UACR (x3)		x	x	x	x	DS	DS	DS
	Biomarkers		x	x		DS	DS		
Group	Immediate Start		x	x	x				
	Delayed Start		x	x	x	x	x	x	x

*CBC, Renal Panel, Ferritin, TSAT

** V1 if consent: CBC & eGFR panel

DS = Delayed Start ONLY

This is a two-arm, open-label, single-center, randomized controlled trial to understand the mechanisms of EIH. Participants will be randomized based on stratum of baseline level of urine albumin/urine creatinine ratios (UACR) measured on three consecutive days. The primary analysis will compare the 80 participants in the early start group to the 80 in the delayed start (DS) or waitlisted group over the first 12 weeks. All procedures will be performed as listed in the table based on study visit. Confirmatory analysis will compare the first 12 weeks to the next 12 weeks in the DS group. Accordingly, the study procedures labeled DS will be performed only in the delayed start randomized participants.

Study Intervention

Participants with CKD and anemia who meet the inclusion and exclusion criteria will be randomized to either the immediate or delayed start group. There are at least 7 study related visits in the early start group, and 11 in the waitlist group. Two consecutive days are needed to perform 24h ambulatory BP monitoring, which will be done twice in the immediate start group and 3 times in the delayed start group. Patients will receive oral iron (ferrous sulfate, 324 mg orally twice daily) if serum ferritin concentration is <100 ng/mL or transferrin saturation is <20%. If clinic BP exceeds either 179 mmHg systolic or 109 mmHg diastolic or if clinic BP raises by >20/10 mmHg compared to baseline, antihypertensive medication dose will be increased or a new antihypertensive will be added.

Participants will be identified in the renal clinic or the electronic medical record system based on estimated GFR and Hgb. At baseline, all participants will have 24-h urine Na measured to assess dietary Na intake.

Treatment Adherence

We recognize the limitations of syringe count, but we will assess treatment compliance with the study drug by performing a syringe count at each of the study visits.

Protocol for the management of anemia

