Harms will be assessed by monitoring changes in weight, eGFR, CBC, clinic BP, and ABPM. For more definitive assessments, including hospitalizations, serious adverse events will be properly completed and sent to the VAMC DMC as requested. Safety of continued participation will be assessed at each study visit. The stop-points will be treatment-emergent severe adverse events that precludes further exposure to the drug, such as an allergic drug reaction, initiation of renal replacement therapy, or death. If the study drug is stopped, the subject will be continued to be studied so as to not violate the intention-to-treat principle.

Participants

Inclusion Criteria

- Stage 3 or 4 CKD defined as eGFR <60mL/min/1.73m² for ≥3 months or persistent albuminuria for ≥3 months; (i) urine albumin to creatinine ratio of more than 30 mg/g; (ii) urine protein to creatinine ratio of more than 150 mg/g; or (iii) at least 1+ dipstick positive proteinuria. ⁸⁸
- 24h ABPM <140/90 mmHg at baseline in the presence or absence of antihypertensive treatment.
- Hgb between 8 and 10 g/dL.
- No treatment with ESA within the previous 3 months.
- Adults, age 18 and older.

Exclusion Criteria

- Need for packed RBC transfusion in the previous 2 months.
- Myocardial infarction, stroke, or hospitalization for heart failure in the past 2 months.
- In the assessment of the investigator, have hematologic, inflammatory, infectious, or other conditions that might interfere with the erythropoietic response.

Retention of Participants

For half of the participants, only 7 visits are needed. For the others, at least 11 visits over 24 weeks of the trial are needed. We will offer \$20 per visit for participation in the trial to offset travel and time costs.

METHODS

Method of Randomization

Participants will be randomized in a 1:1 ratio to either early or delayed treatment (“waitlisted group”) with EPO according to UACR strata. A random permuted block design will be used to avoid imbalance in assignment to the treatment groups over time. A randomization sequence will be generated by the statistician and individually concealed in sequentially numbered opaque envelopes. After confirming eligibility with the principal investigator, the study pharmacist will dispense EPO according to the randomization sequence.

Measurement of clinic BP

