2. Change from baseline to 12 weeks in systolic BP in the comparisons above. Between group change in hypertension status from baseline to 12 weeks. Worsening of hypertension at any time point will be defined either as an increase in BP medication or an increase in seated clinic diastolic BP of ≥ 10 mmHg or systolic BP ≥ 20 mmHg. Within-group change in hypertension status from 12w to 24 w will be compared to the control period of 0 to 12w in the delayed start group.
3. The primary outcome variable in this aim is to examine the change in FMD from baseline to 4 weeks in those treated with EPO compared to the waitlisted group. The hypothesis being tested is that EPO will cause impairment in endothelial function. Accordingly, those on EPO will have worsening of FMD.
4. The primary outcome variable in this aim is to examine the predictors of change in FMD from baseline to 4 w in those treated with EPO compared to time controls. Predictors of this change will be baseline values of the following variables: ADMA, urine nitrate and nitrite, renin, aldosterone, and plasma endothelin-1 and change from baseline to 4 w in the above variables. This analysis will answer the question: which of the pathways independently is predictive of endothelial dysfunction?

Sample Size

The primary objective of the study is to assess the change from baseline to 12 weeks in diastolic BP in EPO treated patients compared to controls. In the waitlisted group, we will measure the change from 12 weeks to 24 weeks compared to the change from 0 to 12 weeks. We have measured 24h

ambulatory BP in 183 CKD patients 4 weeks apart. The mean diastolic BP at baseline was 68.3 mmHg and at 4 weeks 68.1 mmHg. The mean difference was 0.14 mmHg and the standard deviation of the difference was 10.3 mmHg. With these assumptions, two-tailed tests and 80% power, the required sample size to detect a between-group difference of 5 mmHg is 68 subjects completing the study in each group. Assuming 85% of those randomized complete the trial, we would need to randomize $68/0.85 = 80$ subjects per group, or 160 subjects in total.

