- model 1: The outcome variable will be 24h ambulatory diastolic BP. The predictors will be indicator variables for group (early or late start), time (baseline and 12 weeks), stratum (UACR: none, high, very high) and all interactions. The random component of the mixed model will include subject and time. Unstructured covariance will be used with estimation of marginal means by maximum likelihood. We expect the interaction between group by time to be significant. The random coefficient analysis does not require baseline systolic BP as a covariate. If the 3-way interaction term (group x time x stratum) is significant, then results will be reported within each stratum. Confirmatory analyses will utilize change from baseline in clinic diastolic BP.
- model 2: The outcome variable will be 24h ambulatory diastolic BP. The predictors will be indicator variables for period within the delayed start group (early or late), time (baseline and 12 weeks from start of period), stratum (UACR: none, high, very high) and

all their interactions. The random component of the mixed model will include subject and time. We expect the interaction between period by time to be significant. If the 3-way interaction term is significant, then results will be reported within each stratum.

Accounting for missing data

Ambulatory BP recording, the gold-standard to assess BP, is carried out only twice during the trial in the parallel group analysis, but clinic BP measurements occur every 4 weeks. Patients who drop out but have some post-baseline measurements of clinic BP will be included in the analyses, thus minimizing loss to follow up. We will impute ambulatory BP as follows: we will use the complete data to build a model that relates the follow-up mean 24-hour ambulatory diastolic BP from the baseline 24-hour ambulatory diastolic BP and the clinic measures using repeated measures Mixed Model regression - then use the expected value from the model for the missing value - and use PROC MI (which generates maybe 5 replicate values to insert variability into the imputation) so that there is a price to pay for imputing.

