The number of subjects who experience hypokalemia, hypercalcemia, gout, hospitalization for diabetes mellitus, transient elevations in serum creatinine concentration, and symptomatic orthostatic hypotension will be counted for each group and compared using a Poisson regression model using terms for treatment and treatment x stratum. The statistical significance of the treatment term will be used to indicate differences between CTD and placebo. If the interaction term is significant then the event rates will be reported for each stratum. The mean change from baseline in serum potassium, calcium, estimated GFR, uric acid, HgbA1C, PTH intact, and orthostatic BP will be calculated using mixed models as noted above.

Alternative study design considerations and clarifications

Choice of non-dialysis patients. Dialysis patients are challenging to study because it is more difficult to determine hypertension due to confounding by dry weight. Angioaccess makes it difficult to perform FMD. Furthermore, the number of dialysis patients—in contrast to CKD patients not on dialysis—is limited.

Timetable/Milestones

We expect to recruit and randomize a total of 160 participants in the first 3.5 years and complete the study in 4 years. This will require approximately 1 participant to be randomized per week. See table below.

Table 1: Timeline for randomization in the trial (t = 4y, n = 160)

	Year 1				Year 2				Year 3				Year 4			
Quarter	1	2	3	4	1	2	3	4	1	2	3	4	1	2	3	4
Patients	x	16	16	16	16	12	12	12	12	10	10	10	10	8	x	x

Feasibility

A feasibility assessment was performed using data from the Veterans Administration's Corporate Data Warehouse (CDW), a national repository of data compiled from the electronic medical record (EMR) system used by the Veterans Health Administration (VHA). These data include current and historical values from multiple domains such as patient medications, vitals, labs, procedures, and diagnoses, and are available from October 1st, 1999 forward. Of note, these data are updated on a daily basis and are neither filtered nor validated prior to entry into the CDW. We will use these values to screen potentially eligible participants. It is only possible to uniquely identify potential participants by accessing their EMRs using real social security numbers.

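### The safety test applies a Poisson model with treatment x stratum to yes/no events, which gives wrong error rates for common events, non-estimable stratum effects for rare ones, and a treatment term that need not be an overall comparison

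*Combined protocol and SAP*

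**What the plan says.** All references are to the combined protocol and SAP. The relevant text is Statistical Methods, Safety analysis.

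- The quantity compared is subjects with an event: "The number of subjects who experience hypokalemia, hypercalcemia, gout, hospitalization for diabetes mellitus", followed by short-lived creatinine rises and orthostatic symptoms. These counts "will be counted for each group and compared using a Poisson regression model using terms for treatment and treatment x stratum".
- The treatment term is the test of harm: "The statistical significance of the treatment term will be used to indicate differences between CTD and placebo". The treatment names in that sentence do not fit this trial, but that is a separate matter.
- The interaction decides what is reported: "If the interaction term is significant then the event rates will be reported for each stratum".
- Primary Analysis defines three levels, "stratum (UACR: none, high, very high", so there are six treatment-by-stratum cells. Method of Randomization gives the allocation: "Participants will be randomized in a 1:1 ratio to either early or delayed treatment", within UACR strata. The overall trial design section gives 80 participants per group.

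The safety text states no robust variance, stratum main effect, person-time offset or rule for sparse or zero counts. It does not say whether significance is judged by a Wald or a likelihood-ratio test, or how the terms are coded. Elsewhere the plan uses logistic regression for worsening of hypertension and allows Fisher's exact test for small cells in the baseline tables. Neither is carried into the safety analysis.

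**The concern.** Three features of one sentence work against the safety comparison.

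1. Ordinary Poisson regression sets the variance of a count equal to its mean. A count of subjects with a yes/no event has the smaller binomial variance, so for common events the standard errors are too wide and real differences are harder to see.
2. Splitting each event over six cells leaves few subjects per cell. For uncommon events an empty cell is likely, and the stratum effect that depends on it cannot be estimated.
3. Once an interaction is in the model, the treatment coefficient is in general no longer an overall effect, yet the plan uses it as one. Without a stratum main effect, ordinary differences in risk between strata can appear as an interaction and trigger reporting by stratum.

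At stake is whether the published safety comparison has the error rate it claims, and whether a true excess of events is likely to be seen.

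**Working it through.** **Inputs.** From the documents: 80 per group, 1:1 allocation within strata, three strata, and "With these assumptions, two-tailed tests and 80% power" (Sample Size). Assumed: two-sided alpha 0.05, event risks from 2% to 50%, and stratum sizes of either 80/3 = 26.7 per group or an uneven 48/20/12.

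**The plan's own figure.** No figure is given for safety; the group size comes from the diastolic BP calculation. With a 5 mmHg difference and SD 10.3 mmHg, an exact t-test needs 68 per group (power 80.2%), and 68/0.85 = 80. This reproduces.

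**Step 1: variance.** For x0 and x1 events in groups of 80, the model-based Poisson variance of the log risk ratio is 1/x0 + 1/x1. The binomial (robust) variance is 1/x0 + 1/x1 - 2/80. At a common risk p their ratio is 1/(1-p): 1.05 at 5%, 1.11 at 10%, 1.25 at 20%, 1.43 at 30%.

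Example, 20% v 40%: 16 and 32 events are expected. The Poisson SE is sqrt(1/16 + 1/32) = 0.306 and the robust SE is sqrt(1/16 + 1/32 - 2/80) = 0.262. With log 2 = 0.693, z is 2.26 against 2.64.

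Enumerating every pair of binomial counts, with no interaction in the model, gives the exact size of a nominal 5% test (a zero group counts as non-rejection for Wald):

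| Risk | Poisson Wald | Robust Wald | Poisson likelihood ratio |
|---|---|---|---|
| 2% | 0.01% | 0.02% | 8.9% |
| 5% | 0.9% | 1.3% | 7.1% |
| 10% | 2.8% | 3.7% | 4.6% |
| 20% | 2.6% | 4.5% | 3.1% |
| 30% | 1.7% | 4.6% | 2.0% |

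Wald power, Poisson then robust: 10% v 25%, 63% and 70%; 20% v 40%, 66% and 79%; 30% v 50%, 52% and 72%.

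**Step 2: empty cells.** P(at least one empty) = 1 - product over the six cells of [1 - (1-p)^n]. For equal cells at 5% risk: 0.95^26.7 = 0.255, and 1 - 0.745^6 = 0.83.

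| Risk | Equal strata | 48/20/12 |
|---|---|---|
| 2% | 99.5% | 99.8% |
| 5% | 83% | 93% |
| 10% | 31% | 61% |
| 20% | 2% | 15% |

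The chance passes 50% at a risk of about 8% with equal strata and about 12% with 48/20/12.

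A trial fit with 27 per cell and events 1, 2, 0 v 2, 1, 3 reported convergence. The coefficient for the empty cell was -20.3 with SE about 15,400. The treatment coefficient in the reference stratum was finite: 0.69 (SE 1.22).

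**Step 3: what the treatment term measures.** Under reference coding with six free cells, the treatment coefficient compares about 27 with 27 subjects in one stratum. For 20% v 40%, 5.4 and 10.8 events are expected, so the SE is sqrt(1/5.4 + 1/10.8) = 0.527 and z = 1.32. Exact Wald power is about 19%, against 66% for 80 v 80.

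**Step 4: no stratum main effect.** If the interaction is coded as a 0/1 product, all controls share one rate, and the interaction term picks up risk differences between strata among the treated. In 40,000 simulated trials with 27 per cell and no true interaction, it was significant in 30% of runs when stratum risks were 5/10/20% in both groups, and in 28% at 10/20/30%. It was significant in about 5% when all strata had 10% risk.

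**The case against.** The strongest objections, and what stands of them:

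- **The faults do not act together.** This stands. At 2%, 5% and 10% risk the SE is only 1%, 2.6% and 5.4% too wide. At 20% risk an empty cell has a 2% chance with equal strata.
- **Harm tests are not conservative in general.** This stands. A reader might infer that the plan always hides harm. The documents name no test, and at 2% to 5% risk a likelihood-ratio test is too liberal (8.9% and 7.1%). The very low Wald size there comes from sparse counts: a logistic Wald test does much the same (0.02% to 1.3%).
- **The model can be fitted.** This stands. A reader might infer that the specified test is unavailable for rare events. Only the terms that depend on the empty cell lack a finite estimate; other terms and likelihood-ratio tests can be computed. The practical danger is that software reports convergence and the failure goes unnoticed.
- **Coding is not stated.** This stands in part. With 0/1 product coding only the three treated cells are separate, and the chance that one of them is empty falls to about 59% at 5% risk and 17% at 10%. The treatment coefficient then sets one treated stratum against all controls, which is still not an overall comparison.
- **Event rates and stratum sizes are absent.** This stands. Which fault applies to which listed event cannot be settled from the documents.
- **Impact is limited.** This stands in part. Raised BP, the harm of most interest, is analysed by mixed models and logistic regression and does not depend on this model. The other safety events do.

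**Conclusion.** The point holds in limited form: the stated model has a wrong error rate at both ends of the range, for different reasons.

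- At about 20% risk or more, the Poisson variance makes the test conservative (Wald size 2.6% at 20%, 1.7% at 30%) and costs power (66% instead of 79% for 20% v 40%). Below about 10% this fault is small.
- Below about 8% risk with six equal cells, or about 12% with strata of 48/20/12, an empty cell is the usual result. That stratum effect is then not estimable and its Wald test means nothing. At risks of about 5% or less, Wald tests are very conservative and likelihood-ratio tests too liberal, even in a model without strata.
- At any risk, under reference coding the treatment coefficient is not the overall harm test that the plan takes it to be. Without a stratum main effect, the interaction can be significant merely because strata differ in risk.

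The documents do not support the wider conclusions that every harm test is too conservative or that the model cannot be fitted. All magnitudes rest on assumed event risks and stratum sizes, alpha 0.05, and all 80 subjects per group contributing. That the outcome is binary, and that no remedy is pre-specified, rests on the plan's text alone.

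**What to change.** For each event counted as subjects affected:

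1. Report the number and percentage per group and the risk difference or risk ratio with a 95% CI from a UACR-stratified analysis: either Mantel-Haenszel, or Poisson regression with robust variance and stratum as a main effect.
2. Name an exact or score method for sparse events, with the event count below which it applies. Robust variance alone is not enough there: at 5% risk it moves the Wald size only from 0.9% to 1.3%.
3. Take the overall harm test from the analysis without treatment x stratum.
4. Show counts by treatment and stratum descriptively, and delete the rule that makes reporting by stratum depend on a significant interaction.

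The cost is SAP wording and the loss of a formal stratum interaction test for safety events. No extra data, visits or participants are needed.

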On the other hand, HIF stabilizers may raise EPO to more physiologic levels, reduce crosstalk with vascular EPO-receptors, and mitigate hypertension. A 2014 study demonstrated in a rodent model that compared to EPO, treatment with HIF-stabilizer molidustat corrected anemia associated with subtotal nephrectomy. However, in contrast to EPO, molidustat reduced systolic BP in a dose-dependent manner⁸². The authors postulate that anti-inflammatory and anti-fibrotic effects of the drug on the kidney may be operative. This study further illustrates that increment in Hgb can be dissociated from an increment in BP. Human data are available but are thus far inadequate to address the question of risk for or protection from incident hypertension with HIF stabilizers ⁸³⁻⁸⁶.

RESEARCH PROTOCOL AND TRIAL DESIGN

Overall trial design and plan

To test the notion that EPO treatment in anemic patients with CKD and stage 1 or less hypertension that is treated or untreated with antihypertensive medications will raise BP, we propose a randomized controlled trial with a “waiting-list design” as shown in **Figure 2**. In this design, half of the patients are treated immediately with EPO and the other half are put on a waiting list for 12 weeks, after which they begin treatment. Ultimately, the waitlisted patients are exposed to the intervention, thus serving as their own controls. The design allows between-group comparison by comparing responses in the parallel groups over 12 weeks and within-group comparison for the waitlist group in the second 12 weeks compared to the first 12 weeks. Titration of the dose of EPO will occur every 4 weeks to manage anemia as detailed below. The effect of EPO on BP will be assessed by change in diastolic ambulatory BP measured over 24 hours at baseline and again at 12 weeks in both groups and at 24 weeks in the waitlisted group. At baseline and every 4 weeks thereafter, we will also evaluate changes in clinic BP and albuminuria. At baseline and 4 weeks after intervention, we will measure endothelial function, and collect blood for biomarkers. The biomarkers we will be analyzing are renin, aldo, ET-1, catecholamine, ADMA, and urine nitrates and nitrites.

Figure 2: Trial design and study process

Visit		1	2-3	4	5	6-7	8	9	10
Measurement		Consent	Baseline	Week 4	Week 8	Week 12	Week 16	Week 20	Week 24
PROC	FMD		x	x		DS	DS		
HTN	24h-ABPM		x			x			DS
	Clinic BP	x	x	x	x	x	DS	DS	DS
Labs	24h-urine		x			x			DS
	Blood labs*	x**	x	x	x	x	DS	DS	DS

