Comparison of the cohort with these measurements will also be done to understand if the inferences based on the ambulatory BPs accurately reflect the differences between the treatment groups using the clinic BPs. Repeated measures mixed models (PROC MIXED in SAS) will be utilized to assess the overall differences between the treatment groups using the clinic BPs. Additional analyses will explore the nocturnal patterns between the groups in the ambulatory BPs as well as the pattern over time using circadian models of BP in each group.

Between-group changes in hypertension status from baseline to 12 weeks will be tested using logistic regression. Worsening of hypertension at any time point will be defined either as an increase in BP medication or an increase in seated clinic diastolic BP of ≥ 10 mmHg or systolic BP ≥ 20 mmHg. The McNemar test will be used to compare within-group change in hypertension status from 12w to 24 w to that in the control period of 0 to 12w.

To test the hypothesis that EPO is causal to EIH via worsening of FMD, we will evaluate changes from baseline in FMD. That is, we will test if the worsening is a mediation effect using the technique described by Judd and Kenny⁹⁶ and elaborated by MacKinnon⁹⁷. The technique, expanded here for more than one potential mediator employs three regression equations:

- A. $Y = \beta_0 + \tau X_p + \varepsilon$
- B. $X_i = \beta_0 + \alpha_i X_p + \varepsilon$
- C. $Y = \beta_0 + \tau' X_p + \beta_1 X_1 + \dots + \beta_i X_i + \dots + \beta_k X_k + \varepsilon$ for all mediators together,
or $Y = \beta_0 + \tau' X_p + \beta_i X_i \varepsilon$ for each mediator separately

Y is the outcome result (e.g., change in 24-hour diastolic systolic BP), X_p is the group (early vs delayed start) and X_i represent the k purported mediators. The total effect of the treatment on the outcome (measured by the coefficient, τ) is the sum of direct effect (τ') of the treatment and the mediated, or indirect, effects ($\alpha_i \beta_i$). Mediation is established when four conclusions are met: (1) the treatment predicts the outcome variable (supported by a test of statistical significance of τ in equation [A]); (2) the treatment causes the potential mediator (α_i is significant in [B]); (3) the mediator causes the

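### The safety event comparison names arms this trial does not have and sets no time window, although planned follow-up is 12 weeks in one arm and 24 in the other

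*Combined protocol and SAP*

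**What the plan says.** The Safety analysis section lists six kinds of event. The subjects who have them "will be counted for each group and compared using a Poisson regression model using terms for treatment and treatment x stratum". On interpretation it says: "The statistical significance of the treatment term will be used to indicate differences between CTD and placebo". It states no analysis period, person-time or offset. Event rates are mentioned only for reporting by stratum, with no denominator. A further sentence sends the continuous measures to the mixed models described earlier: "The mean change from baseline in serum potassium, calcium, estimated GFR, uric acid, HgbA1C, PTH intact, and orthostatic BP will be calculated".

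The design is set out elsewhere. Under Overall trial design and plan, half of the patients start EPO at once and "the other half are put on a waiting list for 12 weeks, after which they begin treatment". Figure 2 marks the visits after week 12 as delayed start only, and the text beneath it says that "the study procedures labeled DS will be performed only in the delayed start randomized participants". Retention of Participants gives half of the participants 7 visits, and then: "For the others, at least 11 visits over 24 weeks of the trial are needed".

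Other between-group comparisons do carry a window. The primary analysis compares the early group with the "delayed start (DS) or waitlisted group over the first 12 weeks". Hypertension status is also bounded: "Between-group changes in hypertension status from baseline to 12 weeks will be tested using logistic regression".

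**The concern.** The named contrast cannot be carried out, because CTD is defined nowhere and no arm receives placebo. An analyst can still work out that the two randomized groups are meant. The missing window matters more. Taken literally, the sentence counts subjects with at least one event over each group's whole follow-up. The delayed group then has twice the time in which to have an event, and half of that time is on the study drug. A comparison of those counts is not a comparison of EPO with no EPO. Its bias makes immediate EPO look safer than it is.

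**Working it through.** **Inputs from the documents.** There are 80 randomized and 68 completing per arm (Sample Size). Planned follow-up is 12 weeks for immediate start and 24 for delayed start (Figure 2, Study Intervention, Retention of Participants). EPO is given in weeks 0-12 and weeks 12-24 respectively. One sentence under Protocol for the management of anemia expects about half of participants to be treated for 24 weeks, but no immediate-start visit is scheduled after week 12.

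**The plan's own figure.** The safety section gives none. The sample size does reproduce: 2 × (1.96 + 0.84)² × 10.3² / 5² gives 67 per group by the normal approximation and 68 by the t distribution, and 68/0.85 = 80.

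**Person-time.** Immediate: 80 × 12 = 960 person-weeks. Delayed: 80 × 24 = 1920, of which 960 are off EPO and 960 on it.

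**Assumptions.** Let p be the 12-week risk off EPO and q the 12-week risk on EPO. The documents give no event risks, so I take p = 5%, 10% and 20%, and also look lower. There is no dropout or rescue, strata are ignored, and the EPO effect is the same in both arms. The test is the two-sided Wald test on the log ratio of counts, |log(x1/x2)| / √(1/x1 + 1/x2) > 1.96. Rejection rates are summed exactly over two binomials, with zero counts treated as not significant. The 5% level is also an assumption.

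**No EPO effect (q = p), all follow-up counted, independent periods.** Immediate risk is p and delayed risk is 1 − (1 − p)².

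| p | Expected subjects, immediate vs delayed | Ratio | False significance, n = 80 | n = 68 |
|---|---|---|---|---|
| 5% | 4.0 vs 7.8 | 0.51 | 11.7% | 7.9% |
| 10% | 8.0 vs 15.2 | 0.53 | 28.7% | 23.8% |
| 20% | 16.0 vs 28.8 | 0.56 | 46.4% | 39.7% |

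At lower risks with 80 per arm, the rate is 0.5% at p = 2%, 2.9% at 3% and 7.0% at 4%. The ratio stays near 0.5 throughout.

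**The same, with events recurring in the same patients.** With within-patient correlation r between the two period indicators, delayed risk is 2p − p² − r·p(1 − p).

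| r | Ratio at p = 5 / 10 / 20% | False significance, n = 80 |
|---|---|---|
| 0.3 | 0.60 / 0.61 / 0.64 | 6.1 / 15.8 / 24.4% |
| 0.5 | 0.68 / 0.69 / 0.71 | 3.6 / 9.5 / 13.4% |

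**EPO doubles the risk (q = 2p), independent periods.** Ratio = q / [q + p(1 − q)], which is below 1 for any p > 0 and q < 1. Immediate versus delayed risks are 10 vs 14.5%, 20 vs 28% and 40 vs 52%, giving ratios of 0.69, 0.71 and 0.77. The chance of a significant result toward harm is about 0.1% or less.

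**Offset by randomized group only.** Multiplying those ratios by 24/12 gives 1.38, 1.43 and 1.54. A true ratio of 2 is diluted because half of the delayed arm's time is on EPO.

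**Weeks 0-12 only.** With no effect the expected ratio is 1, and false significance is 0.9%, 2.8% and 2.6%. When the risk doubles, the expected ratio is 2.0, with power of 13%, 34% and 66%.

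**The case against.** The strongest reply is that the window can be inferred. Overall trial design and plan describes the between-group comparison in general terms as a parallel one over 12 weeks, and assigns the second 12 weeks to a within-group comparison in the waitlist arm. The BP and hypertension comparisons follow that pattern, and the mean changes in the safety section refer back to models whose between-group form uses baseline and week 12. This stands as evidence of intent. A reader might infer that the plan specifies a 12-versus-24-week comparison, or leaves no way to tell what was meant. Neither is supported. What remains is that the event sentence does not state the window, in a section whose contrast does not belong to this trial.

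The size is also open to challenge, and that challenge stands. The risks are assumed, the inflation falls by about half at a correlation of 0.3, and it is absent for rare events. The documents do not link most of the listed events to EPO, so the doubling case shows the direction of the bias and does not forecast a harm.

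A reader might go further and conclude that harms are otherwise unanalysed. That is not so. Clinic BP, ambulatory BP and worsening hypertension are compared between groups under Primary Analysis and Accounting for missing data, and the ambulatory BP and hypertension-status comparisons run from baseline to week 12. Nor can missing hemoglobin, weight, stroke or cardiovascular tables be called errors. Serious adverse events go to the monitoring committee, by-group descriptive statistics are planned, and the data and safety monitoring plan is not among these documents. The laboratory wording is open, so absence from the schedule does not show that HgbA1C or PTH is not collected.

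**Conclusion.** The event comparison is wrong as written: its contrast does not exist here, and it leaves unstated a window that unequal follow-up makes necessary. Weeks 0-12 was probably intended. If all follow-up were counted instead, the expected ratio under no effect would be about 0.5-0.7 instead of 1. The false-positive rate depends on assumptions: about 12-46% at 5-20% risk with independent periods, about 6-24% with correlation 0.3, and no inflation below about 3% risk. With independent periods and the same EPO effect in both arms, the ratio stays below 1 even if EPO doubles the risk. All of these figures are conditional on the all-follow-up reading. The primary analysis, sample size and patient monitoring are unaffected.

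**What to change.** In the Safety analysis section:

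- Replace the CTD and placebo contrast with immediate versus delayed start.
- Limit the between-group event comparison to weeks 0-12 by randomized group. Waitlisted patients started early because hemoglobin fell below 8 g/dL stay in the group to which they were randomized.
- Give the ratio with its 95% CI, since power is modest even for a doubling.
- Report delayed-start weeks 12-24 separately, as EPO exposure.

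The cost is SAP wording only. No randomized information is lost, because immediate-start follow-up ends at week 12.

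Optional, and not corrections of error: tables of hemoglobin, weight, and stroke or cardiovascular serious adverse events by group, and a check that orthostatic BP, HgbA1C and PTH are in fact collected.
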